Clinicaltrials.gov ID: NCT03712410

Title: A Problem Solving Intervention for Hospice Caregivers

PI: [name]

Date of Document: December 20, 2022

Study Protocol and Data Analysis

Design

The study was designed as a randomized clinical trial with four groups. Hospice caregivers were randomly assigned to either to a group receiving standard hospice care with the addition of the PISCES intervention delivered face to face (Group 1) or a group receiving standard hospice care with the addition of the PISCES intervention delivered in a hybrid format (first session in person, remaining sessions via video) (Group 2) or a group receiving standard hospice care with the addition of the PISCES*plus* intervention delivered in a hybrid format (Group 3) or a group receiving standard hospice care with the addition of the PISCES*plus* intervention delivered entirely online (Group 4).

Setting and Participants

We partnered with Penn Homecare and Hospice Services. Penn Homecare and Hospice Services is an agency (part of the Penn Medicine system) that is Medicare and Medicaid-certified, accredited by the Joint Commission, licensed in the Commonwealth of Pennsylvania. It serves patients and families in Philadelphia, Chester, Delaware, Bucks and Montgomery counties mostly (total number of counties serves is 20) and is experiencing a growth over the years (20% increase in admissions over the past 5 years). The hospice component of the agency had a total number of 2,970 home admissions, an average daily census of 380 and an average length of service (LOS) of 68 days in 2016

Inclusion criteria for caregivers were the following:

- enrolled as a family/informal caregiver of a hospice patient
- 18 years or older
- with access to a standard phone line or Internet and computer access at home
- without functional hearing loss or with a hearing aid that allows the participant to conduct telephone conversations as assessed by the research staff (by questioning and observing the caregiver)
- no or only mild cognitive impairment—mental status will be assessed using the Short Portable Mental Status Questionnaire;¹ individuals with a score of less than seven (i.e., more than three errors) will be excluded, similar to other studies involving this instrument.
- speak and read English, with at least a 6th-grade education

Enrollment

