PISCESplus is meant to be an enhanced version of the PISCES intervention including the original problem solving therapy modules as designed for PISCES with the addition of positive reappraisal elements added to the curriculum. The agenda for the first face to face visit for caregivers (suggested timeline 5-7 days after hospice admission) includes an explanation of the purpose of the visit/call, and confirmation of the three specific problems that the caregiver had selected. During the first session, the interventionist works on steps one and two of the ADAPT model of the PST, namely "Attitude" and "Defining the Problem and Setting Realistic Goals." Additionally, at the end of the first session, the interventionist will ask the caregiver to take the time until the next scheduled session to think about and identify some positive aspects of caregiving, whether these are tasks or responsibilities they enjoy, or other elements of the caregiving experience that they perceive as positive or beneficial.

During the second session (suggested timeline 11-13 days after hospice admission) which took place via video the interventionist covers steps three and four of the ADAPT model. At the end of the session the interventionist asked the caregiver to go over the benefits or positive aspects of caregiving that they had identified and asked them to comment as to why they perceive these as positive or beneficial and whether there are ways to maximize the perceived benefits. The interventionists asked the caregiver to take the time until the next scheduled session to record how the appreciation of these positive elements helps them through stressful situations or when they have negative thoughts.

The third session (suggested timeline 16-18 days after hospice admission) which also takes place via video focuses on step five, namely trying out the solution plan and determining if it works. The interventionist concluded the session by briefly discussing the caregiver's perceived positive aspects of caregiving and reiterating the importance of recognizing and celebrating these aspects during the caregiving trajectory.

Group 4: PISCESplus delivered online

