In this group the entire PISCESplus is delivered online. The first session is conducted via video and not in person (as is the case in Group 3). The agenda for the first video visit for caregivers (suggested timeline 5-7 days after hospice admission) includes an explanation of the purpose of the visit/call, and confirmation of the three specific problems that the caregiver had selected.

During the first session, the interventionist works on steps one and two of the ADAPT model of the PST, namely "Attitude" and "Defining the Problem and Setting Realistic Goals." Additionally, at the end of the first session, the interventionist will ask the caregiver to take the time until the next scheduled session to think about and identify some positive aspects of caregiving, whether these are tasks or responsibilities they enjoy, or other elements of the caregiving experience that they perceive as positive or beneficial.

During the second session (suggested timeline 11-13 days after hospice admission) which took place via video the interventionist covers steps three and four of the ADAPT model. At the end of the session the interventionist asked the caregiver to go over the benefits or positive aspects

of caregiving that they had identified and asked them to comment as to why they perceive these as positive or beneficial and whether there are ways to maximize the perceived benefits. The interventionists asked the caregiver to take the time until the next scheduled session to record how the appreciation of these positive elements helps them through stressful situations or when they have negative thoughts.

The third session (suggested timeline 16-18 days after hospice admission) which also takes place via video focuses on step five, namely trying out the solution plan and determining if it works. The interventionist concluded the session by briefly discussing the caregiver's perceived positive aspects of caregiving and reiterating the importance of recognizing and celebrating these aspects during the caregiving trajectory.

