The primary analyses focused on examining differences between treatment groups in terms of caregiver outcomes during the time of intervention. Changes in caregivers’ scores from baseline to post-treatment will be analyzed using analysis of covariance, with baseline score, site, and whether the caregiver’s patient has died, as covariates. Separate models were run for each outcome (caregiver quality of life, anxiety, depression, and problem-solving ability). For Specific Aim 1 (SA1) to assess the equivalence between PISCES F2F and PISCES in hybrid format, a confidence interval approach was used on the ANCOVA model, with a two-sided 5% level of significance. If the CI of the difference between the two groups falls within the pre-specified range of equivalence, the two interventions will be considered equivalent.^{xiii xiv} The range of equivalence is defined between $-\Delta$ and $+\Delta$. The clinically informed Δ s for the primary outcomes are: CQLI-R = 1.0; GAD-7 = 1.75; PHQ-9 = 2.0; PSI = 2.5, respectively. The analyses of equivalence will be on a per-protocol basis and will be supplemented by secondary sensitivity intent-to-treat analyses.⁵⁵

The analyses for Specific Aim 2 (SA2) focus on pair-wise comparisons between PISCES*plus* and the other treatment groups. A significance level of $\alpha=0.025$ for each comparison was used to account for the multiple (2) comparisons and assure an overall significance level of no more than 0.05 for each outcome. These analyses of superiority was on an intent-to-treat basis, using

multiple imputation to address missing data. ANCOVA and chi-square tests were used to determine whether attrition had an impact on sample composition. Specifically, analyses were computed on baseline demographic characteristics, as well as baseline outcome measures, to determine whether participants who completed all phases of data collection were initially different when compared with persons who did not complete the intervention. Data were analyzed using the Stata statistical package.

Data Analysis for Specific Aim 3

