Our cost analysis compared the three intervention groups with respect to total costs. Using the resource use and cost information, and the cost of client-specific hospitalizations and emergency department visits as described earlier, we estimated the total cost of care for each client. These data were used as the dependent variable in four pair wise regression analyses comparing the four groups with respect to total costs incurred over the study timeframe. Analysis of variance methods was employed. We also examined resource use, and compared this between groups. Specifically, we compared the number of after-hours calls and, and the number of hospitalizations and emergency department visits. As these outcome variables are each an event-count, each cannot be truly normal in distribution. Traditional regression methods assume a normally distributed outcome with constant variance. In contrast, count data are discrete and usually involve many observations with identical values and often highly right-skewed due to a few individuals with extreme event counts. We used both Poisson regression and the Zero-Inflated Poisson model for a comparison of the number of after-hour visits and calls. We also controlled for demographic covariates in these models. Direct and indirect costs for the hospice program were computed as the sum of implementation and operating costs. Intervention implementation costs included equipment costs (based on equipment price and depreciation), and staff training costs. Operating costs were measured by staff costs (wages and time) for delivery of the intervention (based on average wages and average time research staff took to do the intervention), and costs of home visits (frequency and duration) by all hospice staff as documented in the record review. Caregiver costs were based on overall informal care time (using income data gather upon admission), intervention time, any time lost from work, and out-of-pocket and travel expenditures related to caregiving as reported by the caregiver during the exit interview.

Table 1: Participant characteristics

Variable	Traditional Pisces		Online Pisces		
	Group 1 (n = 154)	Group 2 (n = 152)	Group 3 (n = 154)	Online (n = 63)	P-value
Caregiver Age [Mean (Std.)]	56.8 (12.7)	58.8 (12.8)	57.4 (12.2)	56.1 (17.2)	0.5664
Caregiver GAD 7 Score [Mean (Std.)]	6.69 (5.4)	5.74 (4.9)	6.32 (4.9)	5.85 (5.2)	0.4236
Caregiver PHQ-9 Score [Mean (Std.)]	7.54 (5.7)	6.6 (5.4)	6.99 (5.3)	6.78 (5.36)	0.5267

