Taken a job or worked additional hours to earn more money		1 (1.2%)	0 (0%)	2 (2.5%)	2 (5.7%)	
None of these apply		8 (9.8%)	4 (5.3%)	6 (7.5%)	9 (25.7%)	
Decline to Answer		4 (4.9%)	8 (10.5%)	5 (6.2%)	0 (0%)	
Selected More than 1 option		25 (30.5%)	29 (38.2%)	29 (36.2%)	8 (22.9%)	

Table 2. Comparison of 4 groups

Variable	Group 1 Mean (Std)	Group 2 Mean (Std)	Group 3 Mean (Std)	Group 4 Mean (Std)	p-value
Difference (FollowUp-Baseline) GAD-7	-2.54 (4.25)	-1.49 (4.06)	-2.27 (4.56)	-1.52 (5.12)	0.1860
Difference (FollowUp-Baseline) PHQ9	-2.69 (4.29)	-1.56 (4.19)	-1.87 (4.59)	-2.02 (4.14)	0.2752
Difference (FollowUp-Baseline) CLQI	1.14 (6.42)	0.77 (4.82)	0.27 (7.17)	1.15 (5.80)	0.6233

p-value calculated using Kruskal Wallis Test

Table 3. Comparison of Traditional PISCES vs. Online PISCES

Variable	Traditional PISCES Mean (Std)	Online PISCES Mean (Std)	p-value
Difference (FollowUp-Baseline) GAD-7	-2.04 (4.18)	-2.03 (4.74)	0.5638
Difference (FollowUp-Baseline) PHQ9	-2.15 (4.27)	-1.91 (4.44)	0.9848
Difference (FollowUp-Baseline) CLQI	0.96 (5.70)	0.54 (6.76)	0.9169

p-value calculated using Wilcoxon Two Sample Test

Table 4. Within-Group Comparison Baseline vs. Follow-up

Variable	Traditional PISCES Mean (Std)	p-value	Online PISCES Mean (Std)	p-value
GAD-7	-2.04 (4.18)	<0.0001	-2.03 (4.74)	<0.0001
PHQ9	-2.15 (4.27)	<0.0001	-1.91 (4.44)	<0.0001

CLQI	0.96 (5.70)	0.0155	0.54 (6.76)	0.0504
------	-------------	--------	-------------	--------

p-value calculated using Wilcoxon Signed Rank Test

ⁱ Pfeiffer E. A short portable mental status questionnaire for the assessment of organic brain deficit in elderly patients. *Journal of American Geriatrics Society*. 1975; 23: 433-41.

ⁱⁱ Nezu AM, Nezu CM, D'Zurilla TJ. *Solving Life's Problems: A 5-Step Guide to Enhanced Well-Being*. Springer Publishing Company: New York, 2007.

ⁱⁱⁱ McMillan SC, Small BJ, Weitzner M, Schonwetter R, Tittle M, Moody L, Haley WE. Impact of coping skills intervention with family caregivers of hospice patients with cancer: a randomized clinical trial. *Cancer* 2006; 106(1):214-222.

^{iv} Radziewicz R, Rose JH, Bowman K, Berila RA, O'Toole E, Given B. Establishing Treatment Fidelity in a Coping and Communication Support Telephone Intervention for Aging Patients With Advanced Cancer and Their Family Caregivers. *Cancer Nursing*. 2009;32(3):193-202.

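### Tables 3 and 4 label Groups 1+2 and Groups 3+4 as Traditional and Online PISCES; the pooling is unplanned, and the Table 3 contrast isolates neither delivery nor content

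*Combined protocol and SAP*

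**What the plan says.** **Arms.** The Design section gives Group 1 PISCES face to face. Group 2 is PISCES "delivered in a hybrid format (first session in person, remaining sessions via video) (Group 2"). Group 3 is the PISCESplus "intervention delivered in a hybrid format (Group 3"). Group 4 is PISCESplus wholly by video; its section states: "The first session is conducted via video and not in person (as is the case in Group 3"). On content, the Group 3 section says "PISCESplus is meant to be an enhanced version of the PISCES intervention": the problem-solving modules are kept and positive reappraisal is added.

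**Planned analysis** (Data Analysis for Specific Aims 1 and 2). Changes "will be analyzed using analysis of covariance, with baseline score, site" and patient death as covariates. Aim 1 is "to assess the equivalence between PISCES F2F and PISCES in hybrid format", per-protocol with an intent-to-treat sensitivity analysis. Aim 2 is two pair-wise comparisons of PISCESplus with other groups, each at 0.025, by intent to treat with multiple imputation. The plan gives no group numbers for the two Aim 2 pairs.

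**Reported tables.** The header of Table 1 (participant characteristics) carries "Traditional Pisces" and a matching Online label above the group columns, and also heads Group 4 alone as Online, with n = 63. Table 2 gives the four arms by number with a Kruskal-Wallis test. Then comes "Table 3. Comparison of Traditional PISCES vs. Online PISCES", with a Wilcoxon two-sample test. Table 4 gives signed-rank tests within the same two columns. The labels are not defined in the text.

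**The concern.** The column names describe delivery, but a Traditional/Online split does not exist in the design. Groups 2 and 3 share one delivery format; if the columns are Groups 1+2 and Groups 3+4, these two arms sit on opposite sides. A table headed this way, with a GAD-7 difference of 0.01 and p = 0.5638, invites the reading that delivery mode makes no difference. Relabelled as PISCES against PISCESplus, it would invite a reading about content instead. Neither reading is safe, because content and delivery change together across the columns. The contrast also uses an unadjusted rank test where the plan specifies a covariate-adjusted model.

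**Working it through.** **1. Which groups are in which column.** Inputs: n = 154, 152, 154 and 63 (Table 1, participant characteristics); mean change and SD by arm (Table 2).

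Pooled mean = Σnᵢmᵢ / N. Pooled SD = √{[Σ(nᵢ−1)sᵢ² + Σnᵢ(mᵢ−m)²] / (N−1)}.

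Example, GAD-7, Groups 1+2: mean = (154×(−2.54) + 152×(−1.49)) / 306 = −617.64/306 = −2.02. SD = √{[153×4.25² + 151×4.06² + 84.3] / 305} = 4.18, where 84.3 is the between-arm term, (154×152/306)×1.05².

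| Change score | Groups 1+2 pooled | Table 3 Traditional | Groups 3+4 pooled | Table 3 Online |
|---|---|---|---|---|
| GAD-7 | −2.02 (4.18) | −2.04 (4.18) | −2.05 (4.73) | −2.03 (4.74) |
| PHQ-9 | −2.13 (4.27) | −2.15 (4.27) | −1.91 (4.46) | −1.91 (4.44) |
| CQLI-R | 0.96 (5.68) | 0.96 (5.70) | 0.53 (6.80) | 0.54 (6.76) |

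The largest deviations are 0.022 in a mean and 0.039 in an SD. Across all 50 ordered pairs of disjoint sets of arms, the next best (Groups 1+2 against Group 3 alone) misses by 0.27 in a mean and 0.41 in an SD. The split is identified. Table 4 prints the same means and SDs, so it uses the same columns.

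**2. What the columns contain, as assigned, at Table 1 n.**
- Hybrid share of *Traditional*: 152/306 = 50%.
- Hybrid share of *Online*: 154/217 = 71%. Fully online: 63/217 = 29%.
- Video sessions, *Traditional*: (152×2)/(306×3) = 304/918 = 33%.
- Video sessions, *Online*: (154×2 + 63×3)/(217×3) = 497/651 = 76%.
- Positive reappraisal: none of *Traditional*, all of *Online*.

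**3. What the pooled difference mixes.** With mᵢ the mean change in Group i, pooled difference = (154/306)(m₂−m₁) + (m₃−m₂) + (63/217)(m₄−m₃): delivery within PISCES, content within hybrid, delivery within PISCESplus. For GAD-7 the differences in brackets are 1.05, −0.78 and 0.75, so the terms are 0.53 − 0.78 + 0.22 = −0.03 (Table 3 prints +0.01). The small pooled value is a sum of terms of opposite sign. These are unadjusted differences and the four-group p-value is 0.1860, so none of them is shown to be real.

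**4. Whether Table 3 uses the Table 1 n.** Solve each Table 3 mean for the weight of its first arm, allowing ±0.005 rounding in every mean.
- Group 1 share of *Traditional*, GAD-7: (−2.04+1.49)/(−2.54+1.49) = 52.4%, range 51.4–53.3%. PHQ-9 range: 51.3–53.1%. At Table 1 n: 50.3%.
- Group 3 share of *Online*, GAD-7: (−2.03+1.52)/(−2.27+1.52) = 68.0%, range 66.7–69.3%. CQLI-R range: 68.2–70.5%. At Table 1 n: 71.0%.

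These ranges exclude the Table 1 weights, so the analysed numbers differ from Table 1 and are not stated. Hybrid caregivers still make up about two thirds of the analysed *Online* column.

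**5. Planned against reported.** The plan has a Group 1 against Group 2 equivalence contrast and two PISCESplus pairs, all from ANCOVA. Tables 2 to 4 have a four-group rank test, a pooled two-group rank test and pooled signed-rank tests. No adjusted estimate or confidence interval appears.

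**The case against.** The strongest defence is that the documents draw no conclusion from Tables 3 and 4, that the arms appear correctly numbered in Table 2 directly above, and that Aim 2 might mean Groups 3 and 4 taken together as PISCESplus. The first two points stand and limit the matter to labelling and disclosure. The third does not rescue Table 3: even on that reading nothing pools Groups 1 and 2, and neither the Online label nor the unadjusted test follows from the plan.

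Stronger readings that the documents do not support:
- *The planned analyses were not done.* The plan says models were run for each outcome; results may exist elsewhere. What is missing is their report in these tables.
- *The columns have wholly different content.* PISCESplus keeps the PISCES modules and adds to them.
- *Table 4 is confounded too.* It makes no comparison between columns. Only the labelling and not-in-plan points apply to it.
- *Group 4 was imbalanced on bereavement at baseline.* Table 1 does not date that status, and deaths during participation were recorded, so it may have arisen after assignment.
- *Equivalence of Groups 1 and 2 is met, or is refuted.* Unadjusted, at Table 1 n, the GAD-7 difference (Group 2 minus Group 1) is 1.05 (95% CI 0.12 to 1.98), which passes the 1.75 margin; but Group 1 starts higher (6.69 against 5.74) and the plan adjusts for baseline. Adjusting under an assumed follow-up SD does not settle it: at SD 5.4 the lower limit (Group 1 minus Group 2) is −1.67 at Table 1 n and −1.77 at an assumed 80% follow-up. The CQLI-R interval, unadjusted at Table 1 n, is −0.90 to 1.64 against a margin of 1.0. The per-protocol set is not identified.

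**Conclusion.** The point holds as a labelling and disclosure defect that should be fixed. The columns are Groups 1+2 and Groups 3+4; *Online* misdescribes a column in which 71% were assigned an in-person first session, and Table 1 uses the same word for Group 4 alone. Neither the Table 3 contrast nor the pooled Table 4 tests are in the stated plan, and Table 3 cannot support a conclusion about delivery or about content. A reader might infer that the pooling conceals a true delivery or content effect; the unadjusted arm differences do not show one.

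The identification of the columns rests only on the documents' own figures. The 71%, 50%, 33% and 76% are assigned shares at Table 1 n; the analysed shares differ slightly and cannot be fixed without the analysed numbers.

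**What to change.** - Relabel the columns of Tables 3 and 4, and the Table 1 header, as Groups 1+2 (PISCES) and Groups 3+4 (PISCESplus).
- Footnote both tables as not in the stated analysis plan, and Table 3 as confounding content with delivery. Draw no conclusion about either from Table 3.
- State the analysed n per arm and outcome.
- Report the planned ANCOVA contrasts with confidence intervals: Group 1 against Group 2 beside the margins, with the per-protocol set defined, and the two Aim 2 pairs, named. Group 3 against Groups 1 and 2 is one inferred reading; of those two, only Group 3 against Group 2 holds delivery fixed.
- Treat any comparison with Group 4 as exploratory. Disclose that recorded bereavement differs (30.9% in Group 3, 6.4% in Group 4, timing not stated), as does dementia diagnosis (2/45 against 13/23, a row that omits 109 of 154 and 40 of 63 caregivers).
- Make no equivalence statement from the unadjusted tables.

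Relabelling and footnotes cost almost nothing. Defining the per-protocol set and running or retrieving the imputation analyses takes some work on existing data. The planned single-arm contrasts will have wider intervals than the pooled one.
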